### Answer/Response:

Pulmonary function is compromised following upper abdominal surgery. The incidence of post-operative pulmonary complications following upper abdominal surgery ranges between 17% and 88%, and it is a common cause of morbidity and mortality. Physicians order Incentive Spirometry (I.S.) and EzPAP® lung expansion therapy following surgery to encourage improved alveolar ventilation and to reduce risks of post-operative pulmonary complications associated with inhomogeneous distribution of ventilation during deep breathing inspiratory efforts. The primary purpose of this study is to determine if there is a difference in regional distribution of ventilation when comparing resting tidal ventilation with Incentive Spirometry (I.S.) and EzPAP® lung expansion therapy in healthy adult human subjects. We are also interested in determining if regional redistribution of ventilation is time dependent. Lung volume areas of interests include ventral, mid-ventral, mid-dorsal, and dorsal regions. Our null hypotheses is that there is no difference.

A convenience sampling of study participants will be invited to participate in our descriptive observational study. Study participants will be randomly allocated to receive I.S. or EzPAP® therapy after informed consent has been obtained. Electrical Impedance Tomography (EIT) monitoring will be used to visualize and measure regional distribution of ventilation during lung expansion therapy.

EIT lung monitoring and descriptive data will be presented as number (%), mean (SD), or median (IQR) as appropriate. To test our primary hypothesis, the difference between continuous level data will be analyzed with one-way multivariate analysis of variance. This is a proof of concept study that will include 30 human subjects. Statistical significance is set at  $\leq 0.0125$ . We have created a password protected SPSS file (SPSS v.23; Chicago, IL) that will be used for this study's data entry codebook and statistical output generator.

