**Answer/Response:**

The primary purpose of this study is to determine if there is a significant difference in regional distribution of ventilation when comparing eupneic tidal ventilation to Incentive Spirometry (I.S.) and EzPAP® lung expansion therapy in healthy adult human subjects. Electrical impedance tomography (EIT) will be used to measure regional distribution of ventilation during resting tidal ventilation and during lung expansion therapy.

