**Answer/Response:**

The focus of this study is to use electrical impedance tomography (EIT) monitoring to determine if there is a difference in regional distribution of ventilation when comparing Incentive Spirometry (I.S.) to EzPAP® lung expansion therapy.

Baseline characteristics will be reported as:

- Sex (M/F): n (%)
- Age (years): m (SD)
- Weight (BMI): m (SD) or M (IQR) depending upon normality of data distribution
- Tobacco History: n (%); Never smoked, Current smoker; Former smoker
- Respiratory Related Comorbidities: n (%)

Baseline and post-lung expansion therapy dependent variable metrics will be reported as end-expiratory lung volume impedance (EELI) for each of the following ventilation regions of interest:

- Ventral (Level of measurement- continuous)
- Mid-ventral (Level of measurement- continuous)
- Mid-dorsal (Level of measurement- continuous)
- Dorsal (Level of measurement- continuous)

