**Answer/Response:**

**PRIMARY NULL HYPOTHESIS:**

There is no difference in regional distribution of ventilation when comparing Incentive Spirometry (I.S.) lung expansion therapy to EzPAP® lung expansion therapy in healthy adult human subjects

**Alternative hypothesis:** There is a difference in regional distribution of ventilation when comparing Incentive Spirometry (I.S.) lung expansion therapy to EzPAP® lung expansion therapy in healthy adult human subjects?

- Independent variable
  - Lung expansion therapy
    1. Incentive Spirometry

2. EzPAP®

- Dependent variables
  - Regional distribution of ventilation areas of interest
    1. Ventral end-expiratory lung volume impedance
    2. Mid-ventral end-expiratory lung volume impedance
    3. Mid-dorsal end-expiratory lung volume impedance
    4. Dorsal end-expiratory lung volume impedance
- Statistical analysis
  - Frequency (n) and percentage (%) will be used to report descriptive categorical level data.
  - Shapiro-Wilk test of normality will be applied to evaluate distribution of continuous level data. Normally distributed data will be presented as mean and standard deviation and 95% confidence interval. Effect size will be reported as Cohen's *d*.
  - Non-normally distributed data will be reported as median and interquartile range. Effect size will be reported as *r*.
  - Independent samples t-test will be applied to normally distributed continuous data to compare group means, and Mann Whitney-U test will be applied to non-normally distributed data.
  - Statistical significance set a  $P$  (2-tailed)  $\leq .0125$  to reduce risk of Type I error.

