**Answer/Response:**

## Biomedical Research

### 1. What will be done in this protocol?

#### **INSTRUCTIONS:**

This should include everything that will be done as part of this protocol. Do not repeat information that is included in other sections such as Background or Hypothesis sections. This section should include an indication of which research interventions if any offer a prospect for direct benefit and which interventions (invasive measurements, collection of blood, tissue, data, surveys, etc.) are being done solely to answer a research question and generate generalizable knowledge. If the interventions done solely for research purposes are associated with greater than minimal risk they need to be justified. Describe and justify any control and experimental arm and include method, dose, and duration of drug administration. Reference any claim of clinical equipoise if applicable.

If you are obtaining specimens or data, provide information regarding the type of specimen/data, amount of specimen needed and how the specimen/data will be obtained and what analysis will be done with the specimen/data.

Special note for studies with waiver of consent/waiver of documentation of consent:

Include a statement regarding how subjects will be recruited. For other studies this information is captured in Recruitment does not need to be duplicated in this section.

**Answer/Response:** We will use a convenience sampling scheme to identify potential study participants. Documentation of informed consent will be recorded. Electrical Impedance Tomography (Pulmovista 500; Draeger, Lubeck, Germany), which provides non-invasive and radiation free monitoring, will be used to monitor and measure regional distribution of ventilation during I.S and EzPAP® lung expansion therapy. The PulmoVista 500 EIT device has a reported high patient safety profile and poses minimal patient risk. All study procedures will take place at University of Virginia Medical Center, Second Floor, Pulmonary Diagnostics & Respiratory Therapy Services, Room 2025.

[figure not shown]
IRB-HSR # 19661: A descriptive observational pilot study comparing regional distribution of ventilation during lung expansion therapy in healthy human subjects

Procedure set-up and device calibration will occur according to Draeger provided PulmoVista 500 (Draeger; Lubeck, Germany) EIT training and operation manual:

- Study participant preparation

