**Incentive Spirometry procedure**

A study investigator will provide instruction on Incentive Spirometry procedure performance before supervised therapy and monitoring begins.

- Five minutes of eupneic ventilation EIT monitoring will occur before I.S. therapy commences.
- Study participants will be asked to take 10 deep breaths through the incentive spirometer’s mouthpiece, followed by a 60 second pause.
- The 10-breath cycle will be repeated three times with respiratory therapist coaching.
- Five minutes of eupneic ventilation EIT monitoring will occur following the last I.S. lung expansion therapy breath cycle.
- Incentive Spirometry therapy and monitoring session will last about 15 minutes (See image).

[figure not shown]

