**EzPAP® POSITIVE AIRWAY PRESSURE GROUP**

- A study investigator will provide instruction on EzPAP® procedure performance before supervised therapy and monitoring begins. A second study investigator will perform EIT device set-up and monitoring only.
- Five minutes of eupneic ventilation EIT monitoring will occur before EzPAP® therapy commences.
- Study participants will be asked to breathe normally through the EzPAP® device’s mouthpiece for 10 breaths, followed by a 60 second pause.
- The 10-breath cycle will be repeated three times with respiratory therapist coaching.
- Five minutes of eupneic ventilation EIT monitoring will occur following the last EzPAP® lung expansion therapy breath cycle.
- EzPAP® therapy and monitoring sessions will last about 15 minutes (See image).

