**REGIONAL DISTRIBUTION OF VENTILATION MONITORING:**

- PulmoVista monitoring and lung expansion therapy will occur only one time as described above. .
- The following information will be displayed on the PulmoVista 500 device’s main monitoring screen during lung expansion therapy, but study investigator staff administering therapy and study participants will be blinded from information displayed on the screen’s monitor during therapy session in an effort to reduce performance bias:

[figure not shown]
A: Dynamic imaging showing impedance changes in a caudo-cranial image referenced to a dynamic baseline.  
 B: Tidal image showing EELI during inspiration and exhalation of the last detected breath.  
 C: Global impedance waveform showing relative impedance changes across electrode plane.  
 D: Regional impedance waveforms  
 F: Tidal respiratory rate  
 G: Global tidal variation displayed as 100%.  
 H: Regional tidal variation displayed as a percentage of global tidal variation.  
 - Once lung expansion therapy

IRB-HSR # 19661: A descriptive observational pilot study comparing regional distribution of ventilation during lung expansion therapy in healthy human subjects

session has ended, the researcher will detach trunk cables from electrode cables, detach reference electrode snap from adhesive ECG electrode, unclamp the electrode belt, and then remove belt from the study subject. Subject participation in this study is considered complete at this time.

- Inspect of electrode belt contact area will be performed to assess for evidence of skin irritation or bruising. Study participant will be notified by study investigator at the time of skin assessment if significant skin irritation or bruising is present. Finding will be recorded by study investigator.

- Displaying changes
  - The following information will be displayed and used to record pre and post lung expansion therapy end-expiratory lung impedance changes:

- Electrode belt, patient cable, and PulmoVista 500 EIT device (Draeger; Lubeck, Germany) will be removed study participant’s room and returned to a storage location outside of patient care areas.
- Following each EIT to subject interface disconnect, an alcohol, aldehyde, or quaternary ammonium based compound will be soaked on a wipe cloth to disinfect the surfaces of the patient cable, electrode belt, trunk cable, and EIT unit.

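### The primary between-device test carries no baseline covariate although a eupneic baseline is recorded in both arms; adding it is a cheap gain in precision, large or small depending on whether a level or a change in EELI is tested

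*Combined protocol and SAP*

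**What the plan says.** Statistical Considerations, item 4, names lung expansion therapy, with two levels, as the sole independent variable, and EELI in the ventral, mid-ventral, mid-dorsal and dorsal regions as the dependent variables. The test is: "Independent samples t-test will be applied to normally distributed continuous data to compare group means". Mann-Whitney is used where normality fails, and the two-sided threshold is 0.0125. The Brief Summary/Abstract names a different method: "the difference between continuous level data will be analyzed with one-way multivariate analysis of variance". Neither has a baseline term.

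A baseline is nevertheless collected. For Incentive Spirometry: "Five minutes of eupneic ventilation EIT monitoring will occur before I.S. therapy commences". For the other arm: "Five minutes of eupneic ventilation EIT monitoring will occur before EzPAP® therapy commences". Statistical Considerations, item 2, commits to reporting EELI at baseline and after therapy for each region.

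Item 4 does not say whether the tested EELI is a level or a change. Items 2 and 4 read as a level. The section on monitoring regional distribution of ventilation says that the display is "used to record pre and post lung expansion therapy end-expiratory lung impedance changes".

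**The concern.** A pre-therapy value of the same quantity, in the same region of the same subject, is usually the most useful covariate available, and here it needs no extra measurement. The study has 30 subjects and no power analysis (Subjects, item 1; Statistical Considerations, item 3), so interval width largely decides what a proof-of-concept result can show. If baseline and outcome are correlated and the test ignores the baseline, the device difference is estimated less precisely than the collected data allow.

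**Working it through.** **Nothing to reproduce.** The sample size of 30 has no effect size, SD or power behind it. The threshold 0.0125 equals 0.05/4, which fits four regions, though the plan does not state that origin.

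**Inputs from the plan.** Total N = 30, no dropout expected, two parallel arms, two-sided 0.0125.

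**Assumptions.** 15 per arm (no ratio is stated), normal data, equal SDs at baseline and outcome unless noted, and rho, the correlation of baseline with outcome EELI, shown as a range because the documents do not give it.

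**Variance factors for the device difference, in units of (2/15) × SD²:**
- Level, unadjusted: 1, with 28 df.
- Level with baseline covariate (ANCOVA): (1 − rho²) × (1 + 1/26), with 27 df. The 1/26 is the average cost of chance baseline imbalance, 1/(N − 4).
- Change from baseline: 2(1 − rho), with 28 df.

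**Interval half-width** = critical t × √(2/15 × factor). Critical t at 0.0125 is 2.669 (28 df) and 2.676 (27 df). Unadjusted level: 2.669 × 0.365 = 0.975 SD. ANCOVA at rho 0.5: 2.676 × √(0.1333 × 0.75 × 1.0385) = 0.862 SD.

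**Detectable difference at 80% power**, from the noncentral t. The unadjusted level gives 1.292 SD. ANCOVA gives 1.320 × √(1 − rho²), and the change score gives 1.292 × √(2(1 − rho)).

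| rho | Level | ANCOVA | Change | ANCOVA v level | ANCOVA v change |
|---|---|---|---|---|---|
| 0 | 1.292 | 1.320 | 1.827 | 2% worse | 28% better |
| 0.3 | 1.292 | 1.259 | 1.529 | 3% better | 18% better |
| 0.5 | 1.292 | 1.143 | 1.292 | 12% better | 12% better |
| 0.7 | 1.292 | 0.942 | 1.001 | 27% better | 6% better |
| 0.8 | 1.292 | 0.792 | 0.817 | 39% better | 3% better |

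**Break-even against a level.** Set the two expected half-widths equal: rho = √(1 − (2.669/2.676)² × 26/27) = 0.20.

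**Single-trial behaviour.** The break-even concerns expected width. In 60,000 simulated trials per rho, the adjusted interval was the narrower one in about 40% of trials at rho 0.2, 60% at 0.3 and 91% at 0.5.

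**Unequal SDs.** If the outcome SD is 1.5 times the baseline SD, the change-score factor in outcome-SD units is (3.25 − 3 rho)/2.25. At rho 0.5, 0.7 and 0.8 the change score then detects 1.140, 0.924 and 0.794 SD, against 1.143, 0.942 and 0.792 for ANCOVA, so ANCOVA has essentially no advantage there.

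**Allocation.** An uneven split widens every interval but leaves the break-even unchanged, because the imbalance factor depends on total N.

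**The case against.** The strongest objection is that the baseline may already be in the test. The only section describing how the outcome is recorded speaks of pre/post changes, and the figures around it are missing from the text reviewed. A reader might infer from item 4 that the baseline is discarded altogether. The documents do not support that: if a change is tested, the baseline enters by subtraction and most of the gain at high rho disappears. This stands, and the claim is limited accordingly. It does not remove the point, because item 4 never makes change the tested variable and names no covariate under either reading.

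A reader might also infer that the primary test is invalid or biased. It is not: randomisation protects the unadjusted comparison. Nor may the 27% and 39% figures be read as gains this study will obtain, since they need both a tested level and a rho of 0.7 or 0.8.

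Two further limits stand. The calculation covers normal data only, so it says nothing about the gain where the plan would use Mann-Whitney. A single linear baseline slope is also assumed across an arm taking deep breaths and an arm breathing normally through its device, with about 15 subjects each.

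**Conclusion.** The point holds as a cheap improvement. Both stated primary analyses have device as their only term, although a baseline is recorded in both arms. The loss is in precision, and its size depends on an unknown rho. For a tested level, the effect of adjusting runs from about 2% worse in detectable difference at rho 0 to 39% better at rho 0.8, with average break-even near 0.2 and no assurance in a single trial at low rho. For a tested change with equal SDs, the gain is 12%, 6% and 3% at rho 0.5, 0.7 and 0.8. It vanishes at those values if the outcome SD is 1.5 times the baseline SD. All figures assume 15 per arm, normal data and two-sided 0.0125. The recommendation rests on the small worst-case cost against a level and a possibly useful gain, not on any error in a stated figure.

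**What to change.** In Statistical Considerations, item 4, state that each regional EELI is compared between devices by a linear model containing device and the same subject's eupneic-baseline EELI for that region, on the same scale and at one pre-specified window. Report the adjusted difference with its interval. Name a rank-based ANCOVA in advance as the sensitivity analysis, and bring the abstract's MANOVA into line. State before data are seen whether EELI is a level or a change. If only a change from baseline can be recorded, keep the two-group test on the change and say so.

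The cost is wording, one degree of freedom per model, and about a 2% larger detectable difference if rho is near 0 (1.32 against 1.29 SD). No new measurement is needed.

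Three neighbouring matters should be reconciled separately: the Shapiro-Wilk rule for choosing the test, the 95% interval beside a 0.0125 threshold, and the measurement window. On the last, Hypothesis to be Tested says EIT will "measure regional distribution of ventilation during resting tidal ventilation and during lung expansion therapy", whereas Statistical Considerations, item 2, refers to values after therapy. The change proposed here covers the between-device comparison only.

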Evaluating the effectiveness of lung expansion therapy relies upon global parameter measures such as pulse oximetry oxygen saturation and/or arterial blood gas measurements, chest wall auscultation, and assessment of sputum expectoration following therapy sessions. These global parameters do not provide the sensitivity necessary to evaluate regional lung function responses to therapy, as can be viewed with a chest x-ray or CT image. These diagnostic images provide a static view for regional lung volume assessment. They also rely upon the use of radiation. In our study, we will use Electrical Impedance Tomography (EIT) monitoring to measure regional distribution of ventilation during I.S. and EzPAP® lung expansion therapy to better understand how air travels through ventral, mid-ventral, mid-dorsal, and dorsal lung regions and to determine if redistribution of lung volume is time dependent. This non-invasive, non-radioactive/non-radiation producing, technology will provide real time quantifiable data that may be used to explore whether there is a difference in preferential regional distribution of ventilation when comparing resting eupneic ventilation to I.S. and EzPAP lung expansion therapy. We will also evaluate whether there is a difference in regional distribution of ventilation measured immediately after the third lung expansion therapy breathing sequence and post-lung expansion therapy session baseline measurement.

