**PRIMARY RESEARCH QUESTION:**

**Is there a difference in regional redistribution of ventilation when comparing eupneic tidal ventilation during Incentive Spirometry (I.S.) or EzPAP® lung expansion therapy in healthy adult human subjects?**

**Null hypothesis:** There is no difference in regional redistribution of ventilation when comparing eupneic tidal ventilation during Incentive Spirometry (I.S.) or EzPAP® lung expansion therapy in healthy adult human subjects?

**Alternative hypothesis:** There is a difference in regional redistribution of ventilation when comparing eupneic tidal ventilation during Incentive Spirometry (I.S.) or EzPAP® lung expansion therapy in healthy adult human subjects?

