**SECONDARY RESEARCH QUESTIONS:**

**1. Is there a difference in regional redistribution of ventilation measured immediately after lung expansion therapy when compared to regional distribution of ventilation measured 5-minutes after lung expansion therapy?**

**Null hypothesis:** There is no difference in regional redistribution of ventilation measured immediately after lung expansion therapy when compared to regional distribution of ventilation measured 5-minutes after lung expansion therapy?

**Alternative hypothesis:** There is no difference in regional redistribution of ventilation measured immediately after lung expansion therapy when compared to regional distribution of ventilation measured 5-minutes after lung expansion therapy?

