**3. Provide a justification for the sample size used in this protocol.**

Include the anticipated accrual rate, the accrual goal for the study, including accrual goals by strata if appropriate, adjustments for drop-outs etc. and study duration.

**Answer/Response:** Since this is a proof of concept study, we did not perform a power analysis to determine a sample size.

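### Optional: Holm's step-down on the four regional I.S.-versus-EzPAP tests never names fewer regions than the fixed 0.0125 cut-off and keeps the same 5% family-wise bound; the gain is small unless three or four regions differ

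*Combined protocol and SAP*

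**What the plan says.** Statistical Considerations, item 4 (plan for primary variable analysis) sets I.S. against EzPAP on four dependent variables: ventral, mid-ventral, mid-dorsal and dorsal end-expiratory lung impedance. Each is compared by an independent-samples t-test, or by Mann-Whitney U if not normal. Significance is a two-tailed P of .0125 or less, chosen "to reduce risk of Type I error". No family-wise level and no multiplicity method are named. Item 2 confirms that the outcome "will be reported as end-expiratory lung volume impedance (EELI) for each of the following ventilation regions of interest".

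Other sections bear on the point:

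- The Brief Summary/Abstract gives the same 0.0125, but says that the data for the primary hypothesis will be "analyzed with one-way multivariate analysis of variance".
- Hypothesis to be Tested frames the primary question around eupneic tidal ventilation and the two therapies, not I.S. against EzPAP.
- Item 3 says of the 30 subjects that "we did not perform a power analysis to determine a sample size".
- Item 5 (secondary analysis) only refers back to item 4.

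**The concern.** With four tests, a single fixed cut-off of 0.05/4 is the simplest way to bound the family-wise error at 5%, but it is more conservative than it needs to be once one region has been declared different. Holm relaxes the threshold step by step as regions are rejected and keeps the same bound.

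What is at stake is how many regions can be named, not whether the overall null is rejected. Naming regions is of stated interest: the Background wants EIT "to better understand how air travels through ventral, mid-ventral, mid-dorsal, and dorsal lung regions", and the Risk/Benefit Analysis describes dorsal volume as a target of EzPAP. In a study of 30 subjects without a power calculation, sensitivity that costs nothing to collect is worth considering. This is a possible improvement, not an error in the plan.

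**Working it through.** **1. Reproduce the plan's cut-off.** Four tests, two-sided (item 4): 0.05/4 = 0.0125, exactly the stated figure. The Šidák value would be 1 − 0.95^(1/4) = 0.01274, so the figure matches Bonferroni. Sum bound: 4 × 0.0125 = 0.05. Under independence: 1 − (1 − 0.0125)^4 = 0.0491. The 5% family-wise level is inferred from this match.

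**2. Holm on the same p-values.** Order them from smallest to largest and compare with 0.05/4 = 0.0125, 0.05/3 = 0.0167, 0.05/2 = 0.025 and 0.05/1 = 0.05, stopping at the first failure.

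- *Never fewer regions.* Every threshold is at least 0.0125, so any p-value that passes the fixed rule also passes Holm.
- *Same 5% bound.* Suppose m of the four nulls are true. When the first true null is rejected, at least m hypotheses are still in play, so its p-value is at most 0.05/m. The chance of that is at most m × 0.05/m = 0.05, whatever the correlation, if each p-value is valid.
- *Same global decision.* The first threshold is 0.0125 under both rules.

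Illustration: p = 0.010, 0.015, 0.020, 0.040. The fixed rule names one region (only 0.010 ≤ 0.0125). Holm names four (0.010 ≤ 0.0125, 0.015 ≤ 0.0167, 0.020 ≤ 0.025, 0.040 ≤ 0.05).

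**3. Size of the gain.** The documents give no effect size, SD, between-region correlation or allocation ratio, so these are assumed: 15 per arm, normal data, pooled t-tests, equal correlation 0.3, and the same standardised difference in every differing region. Simulation with 100,000 trials per cell (standard error at most 0.16 points). Per-region power, fixed → Holm, in %:

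| Regions truly different | 0.5 SD | 0.8 SD | 1.0 SD | 1.3 SD |
|---|---|---|---|---|
| Four | 11.4 → 13.1 | 33.5 → 40.3 | 53.4 → 63.8 | 80.5 → 89.7 |
| Three | 11.5 → 12.5 | 33.4 → 37.1 | 53.4 → 59.0 | 80.5 → 85.8 |
| Two, opposite directions | 11.6 → 11.8 | 33.5 → 34.8 | 53.4 → 56.1 | 80.5 → 83.3 |
| One | gain about 0.1 points | | | |

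Over correlations of 0 to 0.6, the gain at 1.0 SD is 9.5 to 10.9 points (four regions), 5.3 to 5.8 (three) and 2.3 to 2.6 (two). With one region it is 0.2 or less at every effect size. A 12/18 split at 1.0 SD and correlation 0.3 gives a similar picture: 51.4 → 61.5 (four), 51.4 → 56.9 (three), 51.5 → 54.0 (two, opposite), 51.4 → 51.5 (one).

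A separate simulation at 1.0 SD and correlation 0.3 gave the chance of naming every differing region: 32.6 → 37.5% (two), 22.2 → 33.7% (three), 16.2 → 38.4% (four).

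The chance of at least one significant region with four differing is the same under both rules: 33.4%, 71.1%, 88.9% and 98.8% at 0.5, 0.8, 1.0 and 1.3 SD.

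**4. Size of the cost.** Chance of naming at least one truly unaffected region, fixed → Holm, in %, correlation 0.3:

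| Regions truly different | 1.0 SD | 1.3 SD |
|---|---|---|
| Three | 1.3 → 3.0 | 1.2 → 4.1 |
| Two | 2.5 → 3.6 | 2.5 → 4.2 |
| One | 3.5 → 4.2 | 3.5 → 4.4 |

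With no true difference, both rules give 4.9%, 4.7% and 4.1% at correlations 0, 0.3 and 0.6. In a wider grid the highest Holm value was 5.2% (three regions at 2.0 SD, correlation 0.9; standard error 0.13 points). That is (5.2 − 5.0)/0.13 ≈ 1.5 standard errors above the theoretical bound, which is simulation noise. A smaller null run (4,000 replicates) using the plan's Shapiro-Wilk rule to choose between t and Mann-Whitney gave 4.0% to 5.0% for both rules, with normal and lognormal data.

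**The case against.** The case for leaving the plan alone is reasonable.

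- **There is no defect.** The fixed cut-off already bounds the error at 5%, a statistician was consulted, and the decision on the single global null cannot change. All true, and the reason this is only optional.
- **The stated regional interest is a loose fit.** The Risk/Benefit Analysis singles out the dorsal region, and if only that region differs the gain is about 0.1 points. The Background's interest is tied largely to eupneic breathing against therapy and to timing. This weakens the motivation without removing it: the plan still tests and reports four regions.
- **Equal effects flatter a step-down rule.** At correlation 0.3, differences of 1.0, 0.5, −0.5 and −1.0 SD give average per-region power of 32.6 → 36.5%. A dorsal-dominant pattern (−0.3, 0, 0.3, 1.0 SD) gives 20.7 → 21.2%, with more regions named in only 2.0% of trials. This stands: the 8 to 11 point gains need four regions with similar, large differences.
- **It is a trade.** Error among unaffected regions can more than triple (1.2 → 4.1%), and a region can be declared at p = 0.05 when the other three have already been rejected. The 5% target itself is inferred. A sponsor who wants the stricter rate may keep the fixed rule.
- **Intervals.** Holm has no simple matching simultaneous intervals, whereas the fixed rule pairs with 98.75% intervals. The loss is small here, because item 4 plans 95% intervals, which do not match 0.0125 anyway.
- **It is premature.** The primary contrast and test are not settled, and item 4 does not say whether raw post-therapy values or changes are compared. This stands, so the change is conditional on settling them first.

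**Conclusion.** The point holds as an optional improvement. For the four I.S.-versus-EzPAP regional tests, Holm names at least every region that the fixed rule names and keeps the family-wise error within 5% under any dependence, given valid p-values. Neither property depends on the simulation assumptions.

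The size of the benefit does depend on them. Under equal effects, correlation 0 to 0.6 and 15 per arm, the per-region gain is negligible with one differing region and at most about 3 points with two. At 0.8 to 1.3 SD it is roughly 3 to 6 points with three and 6 to 11 with four. It shrinks near 0.5 SD and with unequal effects. Nothing in the documents says which pattern to expect. The bound covers these four tests only, not the secondary tests or the MANOVA.

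**What to change.** First reconcile the primary analysis. State whether the primary comparison is I.S. against EzPAP (item 4) or eupneic ventilation against therapy (Hypothesis to be Tested), and whether the MANOVA of the Brief Summary/Abstract is kept and at what level.

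If the four regional tests remain, replace the significance bullet in item 4, before any outcome data are seen, with:

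> The four regional I.S.-versus-EzPAP p-values will be tested by the Holm procedure at a family-wise two-sided 0.05; Holm-adjusted p-values will be reported.

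Make the 0.0125 sentence in the Brief Summary/Abstract agree. Keep the explicit naming of the I.S.-versus-EzPAP tests, because item 5 refers back to item 4 and would otherwise inherit the rule by default. No Holm family is proposed for the secondary question, which concerns redistribution "measured immediately after lung expansion therapy when compared to regional distribution of ventilation measured 5-minutes after lung expansion therapy": the plan does not say whether the arms are pooled, so the number of secondary tests is not fixed.

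The cost is two sentences and a calculation that can be done by hand, with no added subjects or measurements. What is given up is the lower error rate among unaffected regions and the simple 98.75% intervals.
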